# JHM IRB - eForm A – Protocol

- Use the section headings to write the JHM IRB eForm A, inserting the appropriate material in each. If a section is not applicable, leave heading in and insert N/A.
- When submitting JHM IRB eForm A (new or revised), enter the date submitted to the field at the top of JHM IRB eForm A.

\*\*\*\*\*

# 1. Abstract

In an attempt to decrease wound infection incidence and improve healing time of open surgical wounds, vacuum assisted closure (VAC) was developed. This innovative technique provided contained controlled wound irrigation without bacterial aerosolization. A newer customizable subset of the Prevena incision Management SystemTM called Prevena Peel and PlaceTM has been released a few months ago. The new model can be cut to specific wound sizes and has a connector that can be attached to the already widely available VAC machines. The versatility and the comparability to older models of Prevena Peel and PlaceTM have not been tested to this date.

We believe that a randomized clinical trial evaluating the use of the Prevena Incision Management SystemTM for homecare and the use of Prevena Peel and PlaceTM for inpatients in special populations is warranted. Obese patients (BMI≥30) undergoing open surgery will have decreased surgical site infection rates, improved healing time, better quality of life (QOL) and lower readmission rates with use of Prevena in the post-operative management of surgical incisions.

2. **Objectives** (include all primary and secondary objectives)

**Specific Aim 1:** To determine whether application of an incisional wound PrevenaTM dressing (peel and place or customizable) in the obese (BMI  $\geq$ 30) surgical patient will reduce surgical site infections (SSI) when compared to the standard of care dressing.

**Hypothesis 1A:** Obese patients (BMI  $\geq$ 30) who undergo any elective open surgery will have a significant reduction in SSI and other wound complications (such as dehiscence, seroma and hematoma) when compared to the standard of care dressing presently used.

**Brief Methodology:** Obese patients who are scheduled to undergo any elective open surgery are eligible and have consented and enrolled in the study will be randomized to undergo either incisional wound PrevenaTM or standard of care dressing application immediately following the surgical procedure.

**Specific Aim 2:** To determine whether obese patients who have incisional wound PrevenaTM applied during their surgical procedure have a lower skin bacterial count upon removal of PrevenaTM as compared to those obese patients who had a standard of care dressing placed.

**Hypothesis 2A:** Obese patients who have the Prevena system applied to their incision will have a lower bacterial skin count upon removing Prevena on post-operative day #5-7 as compared to those who had a standard of care dressing placed.

**Specific Aim 3:** To determine whether obese patients who have incisional wound PrevenaTM applied during their surgical procedure have better quality of life assessment as compared to those obese patients who have a standard of care dressing.

**Hypothesis 3A:** Obese patients who have the Prevena system applied to their incision will experience less wound complications and improved quality of life scores using the SF-36 (appendix A).

**Specific Aim 4:** To determine whether obese patients who have an incisional wound PrevenaTM applied during their surgical procedure have decreased readmission rates compared to those obese patients who have a standard of care dressing.

**Hypothesis 4A:** Obese patients who have the Prevena system applied to their incision will experience a decreased readmission rate within 30 days of the operation.

**The primary outcome measure:** the incidence of postoperative surgical site infection (according to CDC/NHSN protocol) in open surgery.

**The secondary outcome measures:** other wound complications (such as dehiscence, seroma and hematoma), skin bacterial count after treatment, wound healing time, quality of life reporting and readmission rates between the two groups.

# 3. Background

Surgical site infections (SSI) are one of the most common postoperative complications accounting for 38% of all nosocomial infections. (1) SSI lead to prolonged hospitalization by approximately 10 days and a 2 to 3 fold increase in health care costs. (2–4) With the introduction of laparoscopic surgery, endovascular surgery, improved sterilization, dressing techniques and antibiotic prophylaxis, there has been a marked decrease in SSI. However, not all surgical procedures can be performed with minimally invasive techniques and still many surgeries performed worldwide today are via an open incision, leaving special populations (obese and diabetic surgical patients) with continued high SSI rates.

Patient-related risk factors for surgical wound infections include age, diabetes, smoking, compromised immunity and obesity. (5) It is well-documented in the literature that obesity is associated with stress, anxiety and depression, all situations which can cause an impaired immune response and as a result delayed wound healing. (6) Moreover, local factors such as decreased vascularity in adipose tissue, friction, skin folds harboring micro-organisms and increased wound tension all lead to impaired healing in obese patients. (7)

Bariatric patients undergoing open Roux-en Y gastric bypass surgery have an estimated surgical site infection rate of 10-20%. (8,9) Obesity by itself is estimated to increase the risk of developing surgical site infection 2 fold. (10) In addition, vascular surgery patients seem to have similar wound infection rates. Groin incisions in vascular surgery have an overall SSI rate higher than predicted by Center for Disease Control National Nosocomial Infections Surveillance Risk Category System, and it reaches 10% to 20% after lower-limb bypass grafting procedures.(11)

In an attempt to decrease wound infection incidence and improve healing time of open surgical wounds, vacuum assisted closure (VAC) was developed. The original study reported enhanced bacterial clearance

and improved tissue granulation. (12) The use of VAC in selected patient groups such as the elderly, diabetics and infected abdominal wounds has gained substantial popularity in the last 5 years.

Recently, similar techniques were employed in the Prevena Incision Management SystemTM for use on *clean closed surgical incisions*. Initial results in Plastic surgery comparing the use of Prevena versus standard dressing for skin flaps had better SSI rates (3% vs 20%).(14) Similarly, a study in vascular surgery patients found a large difference in SSI occurrence (6% Prevena vs. 30% non-Prevena, P<0.0011). (15)

We believe that a randomized clinical trial evaluating the use of the Prevena Incision Management SystemTM (both the peel and place and customizable options) for patients in special populations is warranted. Obese patients (BMI≥35) undergoing any open surgery will have decreased surgical site infection rates, improved healing time, better quality of life (QOL) and lower readmission rates with use of Prevena in the post-operative management of surgical incisions.

# 1. Study Procedures

a. Study design, including the sequence and timing of study procedures (distinguish research procedures from those that are part of routine care).

Prospective single blinded randomized clinical trial.

#### Screening

Candidates will be screened for eligibility for the study when evaluated for any of the surgical procedures described by the PI and CO-PIs. The screening will take place in inpatient or outpatient clinic at either Johns Hopkins Bayview Medical Center or Johns Hopkins Hospital. These surgeries will be elective in nature. Women of child bearing age will be given a urine pregnancy test preoperatively as per standard of care. Those who are pregnant or plan on becoming pregnant for the duration of the study are excluded. Candidates who meet the general inclusion / exclusion criteria will be approached for consent. All HIPAA patient privacy regulations will be observed during discussions with patients.

#### Consent

Patients will be recruited by the surgery services at Bayview Medical Center or Johns Hopkins Hospital. Patient history and routine preoperative tests will be used to identify comorbidities (such as diabetes, immunosuppression and smoking). Hopkins IRB approved consent designee for this study will meet with the patients prior to the operation to discuss the purpose of the trial and the subject's role, should they choose to participate. The patient will be informed in detail about the study and all their questions will be answered before signing the consent form. The patient will be given ample time to consider the study and will also be given a chance to review the informed consent form (ICF). They will have the option of taking the ICF home or having it mailed or emailed to them before making any decisions. No study related procedures would be performed before written informed consent process. All HIPAA privacy regulation applies here and patient rights as well as responsibilities are incorporated in the informed consent process.

#### Enrollment

Once enrolled, patients will be randomized to one of two groups: one group will receive an incisional wound Prevena (experimental) while the other group will receive the standard dressing (control). Randomization will be divided into 4 strata based on the patient's diabetes and smoking statuses (Diabetic smoker/ diabetic non-smoker/ non-diabetic smoker/ non-diabetic non-smoker). The 4 strata have been computer-generated using a in a 1:1 ratio of Prevena vs standard dressing in each

# strata. Given the sample size of the study each strata has been generated to include up to 60 patients. A patient is considered enrolled after he/she has been randomized.

# Peri-operative wound management Antibiotic Prophylaxis:

All patients will receive perioperative standard of care intravenous antibiotics at the surgeon's discretion. The antibiotics will be given for 24 hours following surgery.

All patients will be prepped and draped in the normal sterile fashion using Chlorhexidine skin prep.

The incisions will be made using a skin knife. Both groups will undergo approximation of the subcutaneous tissue using 2.0 or 3.0 Vicryl interrupted sutures. For skin closure:

1) The incisions will be re-approximated using skin staples at least 1 cm apart (to allow drainage from the subcutaneous tissue).

OR

2) 2.0/3.0 Nylon interrupted or vertical mattress sutures at least 1 cm apart (to allow drainage from the subcutaneous tissue) will be used.

# Swabbing (Bacterial Wound Cultures)

On the day of surgery while in the operating room, once the skin has been closed and just prior to placing the sterile dressing / Prevena, a moistened swab is applied to the wound starting at the most superior/proximal aspect of the incision and running it along the incision line for the length of the incision then rotating the swab 180 degrees and applying the moistened swab from the inferior/distal end of the incision and running it back along the incision line.

After swabbing and according to the randomization, either a NPWT **Prevena**TM or sterile gauze and a transparent film dressing will be applied to the incision.

# Postoperative wound management

As it will be stated and agreed upon in the informed consent, the dressings in both groups will be removed on post-operative day(POD) # 5-7 (or sooner if redness or signs of infection are noted), by the provider/research coordinator in the clinic or on the ward if they are an inpatient. Then the provider/research coordinator will repeat the swabbing procedure mentioned above. Once swabbing is complete, an NP or a PA who are blinded to the study, will come in and asses the wound for healing, infection and other complications.

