# b. Secondary outcome variables:

- 1. Other wound complications (such as dehiscence, seroma and hematoma)
- 2. Skin bacterial count after treatment

- 3. Wound healing time
- 4. Quality of life scores (SF-36 or VQL)
- c. Statistical plan including sample size justification and interim data analysis.

Power and sample size were calculated using SamplePower 2, alpha set at .05, and power of at least 80%. Current literature values suggest a similar SSI rate of 17-24%.(14, 15)

The use of Prevena has been tested in a small retrospective study (52 Prevena devices) of groin incisions in vascular surgery that yielded a large difference of 24% in SSI rates (Prevena 6%, Non-Prevena 30%).(15) Another retrospective study of Prevena use in plastic surgery showed a difference of 17% in SSI rates in patient groups receiving skin grafts (Prevena 3%, Non-Prevena 20%).(14) However, to this date the use of Prevena has not been documented in obese patients.

For a difference of 24% between control and Prevena groups, 27 patients per group (N=54) are needed to achieve power of 80%. Decreasing the group difference to 20% requires 39 patients per group (N=78) for power of at least 80%. Decreasing the group difference even further to 17% requires 54 patients per group (N=108) for power of at least 80%. To detect a smallest difference of 17%, we estimated the need for a total of 108 patients to be enrolled in this study.

- d. Early stopping rules.
  - 1. Inability to tolerate the Prevena Wound VAC
  - 2. Allergic reaction to the Prevena Wound VAC
  - 3. Evidence of wound infection during the use of Prevena Wound VAC
  - 4. Fever of >38.0 during the time the Prevena Wound VAC is in place (the wound VAC should be removed and infection of the skin ruled out)
  - 5. Statistical evidence that the Prevena Wound VAC has better outcomes versus the standard of care wound dressing\*

\*we will carry out a review of the outcomes every 6 months in this study

In order to alleviate the possibility of diabetes and smoking influencing a patient's wound healing outcomes, we stratified our randomization groups into 4 strata:

- 1) Diabetic Smoker
- 2) Diabetic Non-smoker
- 3) Non-diabetic Smoker
- 4) Non-diabetic non-smoker

Given our sample size we ran the randomization schemes for up to 60 patients in each strata.

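### The Aim 2 removal swab is taken by staff who can see the treatment arm, and the blinded NP/PA enters only afterwards

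*Combined protocol and SAP*

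**What the plan says.** Aim 2 (Objectives) asks whether Prevena patients "have a lower skin bacterial count upon removal of PrevenaTM as compared to those obese patients who had a standard of care dressing placed". The time is set by Hypothesis 2A: they "will have a lower bacterial skin count upon removing Prevena on post-operative day #5-7". Study Statistics, item b, lists "Skin bacterial count after treatment" among the secondary outcomes.

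The order at the day 5-7 visit is set under Postoperative wound management:

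- In both groups the dressing is removed "by the provider/research coordinator in the clinic or on the ward if they are an inpatient".
- Next: "Then the provider/research coordinator will repeat the swabbing procedure mentioned above".
- Last: "Once swabbing is complete, an NP or a PA who are blinded to the study, will come in and asses the wound".

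The technique is described under Swabbing (Bacterial Wound Cultures): "a moistened swab is applied to the wound starting at the most superior/proximal aspect of the incision". The swab is then run the length of the incision, turned 180 degrees and run back. The same section names the two dressings: a negative-pressure device, or gauze with a transparent film.

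Follow Up gives the NP/PA, there described as blinded to treatment group, the wound examination only. Section c on blinding justifies it by participant bias and does not mention the swab taker.

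**The concern.** The swab is the whole measurement for Aim 2, and it is taken by hand. How many organisms are recovered depends partly on how firmly, how slowly and how wet the swab is drawn. If the operator knows the arm, expectation can influence those choices. The plan records a favourable view of the device: Innovations and Limitations calls it very promising and reports good experience from pilot patients. That section also hopes that the bacterial count will strengthen the case that Prevena reduces infection.

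The plan already brings a blinded clinician to this visit, but only after the Aim 2 sample has been taken. A difference in technique between arms would enter the comparison directly. The swab taken before dressing cannot correct for it, because the difference would arise days later, at removal. No variable in the plan records technique.

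**Working it through.** **Who knows what, and when**

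| Step at day 5-7 | Who | Knows the arm? |
|---|---|---|
| Dressing removed | Provider/research coordinator | Yes, the dressings are visibly different |
| Swab taken | Provider/research coordinator | Not shielded; no section says otherwise |
| Wound assessed | NP/PA | Stated to be blinded |

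The text names a role, so it does not strictly say that one individual does the first two steps. This changes little, because nothing keeps a second person in that role from seeing the dressing.

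**What the technique leaves open**

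- Fixed for both arms: starting point, full length of the incision, 180-degree turn, return path.
- Not fixed: pressure, speed, amount of moistening.

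**Sensitivity of the comparison (illustration only)**

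The plan has no figure to reproduce: it gives no SD, measurement scale, analysis or power for this outcome.

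Inputs:

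- n = 54 per arm (Study Statistics, item c).
- Assumed: analysis on log10 counts, two-sided z-test at 5%, SD of 0.8, 1.0 or 1.5.
- Assumed: a pure technique shift d of 0.2 or 0.3 log10 between arms, with no true effect.

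Formulas: SE = SD × √(2/54). The chance of a false significant result is P(|Z| > 1.96) when Z has mean d/SE and variance 1.

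Example with SD 1.0: SE = √(2/54) = 0.192. For d = 0.2, d/SE = 1.04. The upper tail is P(N(0,1) > 0.92) = 0.179 and the lower tail is about 0.001, which gives 0.180.

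| Assumed SD | SE | d = 0.2 | d = 0.3 |
|---|---|---|---|
| 0.8 | 0.154 | 0.255 | 0.495 |
| 1.0 | 0.192 | 0.180 | 0.344 |
| 1.5 | 0.289 | 0.107 | 0.180 |

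These shifts are not small on the count scale. Since 10^(-0.2) = 0.63 and 10^(-0.3) = 0.50, they mean about 37% and 50% fewer organisms recovered in one arm, on average over all its patients.

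**The case against.** The strongest reply is that the harm is assumed. The procedure is written down and is the same in both arms. The result is a culture count, not the operator's opinion, and no section suggests that technique would differ by arm. Operator variation unrelated to arm adds noise but does not raise the false-positive rate in this way. All of this stands, so the percentages above show sensitivity and do not predict bias. A reader might infer that the Aim 2 result will be biased, or that its error rate is really 18% or 34%. The documents do not support that, because neither the shift nor the SD has a basis in them.

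A second reply is that the plan put its blinded assessor where clinical judgement matters most. That is also fair. A reader might infer that the primary infection outcome shares this weakness. It does not follow: the swab order affects only the bacterial count, and the day 5-7 wound assessment is assigned to the blinded NP/PA.

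Third, reordering the steps raises practical questions. Dressings may come off early for redness or suspected infection (Postoperative wound management; Risks), and the plan does not promise a blinded NP/PA then. Postoperative wound management describes the NP/PA as blinded to the study itself, and handing that person a research swab would reveal that the patient is a participant. The patient, who wore the dressing, is in the room and may mention it. Skin marks may also reveal the arm, a risk that the wound assessment already carries. These points shape the fix but do not remove the reason for it.

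**Conclusion.** The point holds as an inexpensive improvement to the blinding of one secondary outcome. The Aim 2 swab is taken by a role that is not shielded from the arm, and some elements of technique are left to the operator. A blinded clinician is already due at the same visit. A between-arm difference in technique is possible and could not be removed afterwards; its size is unknown.

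Two inferences support this. The first is that removing visibly different dressings reveals the arm. The second is that the NP/PA could take the swab: the documents give no reason against it, but they do not discuss it. The conclusion does not depend on the assumed shifts and SDs.

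**What to change.** Under Postoperative wound management, set this order:

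1. The provider/coordinator removes the dressing and takes it out of sight.
2. The NP/PA enters, takes the swab by the procedure already written under Swabbing, and then assesses the wound.
3. The patient is asked beforehand not to say which dressing was used.

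In the same paragraph, describe the NP/PA as blinded to treatment group, as Follow Up does, in place of blinded to the study.

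For unscheduled early removals, use the same order when a blinded NP/PA is available without delaying removal or care. Otherwise record that the swab was taken unblinded, and repeat the Aim 2 comparison without those swabs as a sensitivity analysis.

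Cost: a few sentences in the procedures, a short swabbing instruction for the NP/PA, and one recorded item for early removals. Scheduled visits need no additional staff, and there are no additional visits or patients. Blinding is improved but not guaranteed, since skin marks or the patient may still reveal the arm. Labelling tubes by study number only is an optional addition, separate from this point.

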# Follow Up

The patient will be advised to contact the hospital if any of the following signs develop at any time after the procedure (before and in between follow ups):

- a. Fever
- b. Warm, red, painful, swollen wound
- c. Blood or pus coming from the wound
- d. Foul odor coming from the wound

- 1) **POD #1-2:** The patient will receive a personal interview within 24-48 hours of the surgery while still hospitalized by an RN. A Short-Term Prevena Recovery Questionnaire (appendix B) will be completed during the interview regarding the patient's recovery. The most important questions will be tailored towards identifying any allergic reaction symptoms to the treatment option. Other questions include: tolerance, nutrition habits, voiding and bowel movements and any signs of wound infection.
- 2) **POD #5-7:** An examination by an independent nurse practitioner or physician assistant who is blinded to the treatment groups will be performed. Any surgical site infections or complications will be diagnosed using the Center for Disease Control and Prevention guidelines. If there are any complications (i.e. delayed healing, infection), the patient will be scheduled for weekly follow up with the NP, PA or MD until complete wound healing.
- 3) **POD #12 to 14:** Patients will return to clinic for staple or suture removal by the surgeon, the NP or PA. A secondary wound assessment will be performed as in step (2). In the same visit an SF-36 questionnaire (appendix A) will be completed by the patient to evaluate the therapy's impact on QOL.
- 4) POD # 30± 5 days: The patient will receive a phone call or personal interview (if still hospitalized) from one of our team members. A Long-Term Prevena Recovery Questionnaire (appendix C) will be completed during the calls regarding the patient's recovery. Questions about any possible wound complications include: incision check-up (changes in wound appearance and any of the signs mentioned above), development of any new symptom (fever, bowel habit changes, and nutrition habits).

Note: This time frame for follow up was chosen because:

- a. It will minimize data lost to follow up.
- b. It will maximize the opportunity for detection of infection, since the majority of SSIs are apparent by postoperative day 3-5.
- c. The standard of care at the Johns Hopkins surgical department includes a post-op check and visit 5 to 14 days following surgery.
- b. Study duration and number of study visits required of research participants.

Based on the annual number of open procedures at John Hopkins Medical Institutes the investigators anticipate completing the inclusion of patients within a two-year period. Therefore, we plan to enroll a total of n = 108 patients over two years.

Each eligible patient will have an equal chance of being in either group (Prevena vs. standard dressing) regardless of age or comorbid conditions. However, at 6-month intervals a statistical analysis will compare covariates between the two groups. If there are any statistically significant differences between the Prevena/Non-Prevena groups in numbers of diabetics, smokers or immuno-compromised patients (such as being on steroids) an attempt will be made to equalize the numbers on both sides for the following 6-month period. Once randomized, the participant will undergo the specified procedure and at the conclusion of the case when the incision is closed have either Prevena vs. Standard of Care dressing applied. The dressing will be monitored over a 5 day period where it will then be removed. The participant will be followed thereafter until their sutures/skin staples are removed (Figure 1).

Each participant will be followed though POD 30-35. This time frame for follow up was chosen because:

- a. It will minimize data lost to follow up.
- b. It will maximize the opportunity for detection of infection, since the majority of SSIs are apparent by postoperative day 3-5.
- c. The standard of care at the Johns Hopkins surgical department includes a post-op check and visit 5 to 14 days following surgery.

Participants will be seen on the day of surgery, POD1-2, POD 5-7, POD 12-14, and POD 30±5 for a total of 5 encounters.

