# 5. Risks

a. Medical risks, listing all procedures, their major and minor risks and expected frequency.

Generally speaking there is minimal risk in participating in this study. If the patient is randomized to the standard of care they will receive our Centers standard of care for incisional wounds. If the patient is randomized to the Prevena incisional wound VAC system they may experience the following:

- 1. Discomfort and inability to tolerate the incisional wound VAC system: In this situation the dressing will be inspected by the Principle Investigator or wound nursing team who will ensure that the VAC system is properly placed and working correctly. In the event that the patient is still unable to tolerate the device, it will be removed and the patient will be excluded from the study.
- 2. Skin abrasion or irritation: If on inspection the skin edges at the incision appear to be red or irritated the incisional wound VAC will be removed and the incision inspected. The patient would be removed from the study.
- 3. Allergic reaction to the device: If at any time during the study the patient appears to have an allergic reaction to the incisional wound VAC device. The Principle Investigator will determine if the dressing needs to be removed and the patient will be removed from the study.Redness or erythema, fever, signs of infection: Should there be any concern for infection under the incisional wound VAC, it will be removed immediately and the incision assessed by the Principle Investigator, Nurse Practitioner or Physician Assistant. Appropriate standard of care will be initiated should the wound indeed be infected. This may include opening and draining the incision, wet to dry dressing changes and antibiotics treatment.
  - b. Steps taken to minimize the risks.

Follow standard surgical procedures and placement of wound dressing or Prevena Wound VAC.

c. Plan for reporting unanticipated problems or study deviations.

All events will be reported to the JHM IRB as required by the JHM IRB reporting guidelines posted on the JHM IRB website.

d. Legal risks such as the risks that would be associated with breach of confidentiality.

There should be no legal risks by participating in this study. None beyond those associated with routine care.

e. Financial risks to the participants.

None beyond those associated with routine care.

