Incision intact Y/N Patient's tolerance to VAC 1=excellent 2=good 3=fair 4=poor NPO Y/N VI Voiding Y/N IIIIIIIIIIIIIIIIIIIIIIIIIIIIIIIIIII	Edema Y/N				7
Patient's tolerance to VAC 1=excellent 2=good 3=fair 4=poor NPO Y/N Voiding Y/N Last name of person completing	Seroma Y/N				1
1=excellent       2=good       3=fair       4=poor       NPO Y/N       Voiding Y/N       Last name of person completing	Incision intact Y/N				1
Voiding Y/N Last name of person completing	1=excellent 2=good 3=fair 4=poor	c			_
Last name of person completing					_
	Last name of person com evaluation				_
Time to first ambulation following surgery (specify unit please): Comments					

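### The POD 1-2 form (Appendix B) lacks the allergy-symptom and bowel-movement items that the Follow Up text promises, and it grades tolerance for the VAC only

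*Combined protocol and SAP*

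**What the plan says.** Under Follow Up, item 1, a nurse interviews each patient in hospital 24 to 48 hours after surgery. The instrument is named: "A Short-Term Prevena Recovery Questionnaire (appendix B) will be completed during the interview regarding the patient's recovery". Its main purpose is stated next: "The most important questions will be tailored towards identifying any allergic reaction symptoms to the treatment option". The phrase about the treatment option covers either arm. The remaining content follows: "Other questions include: tolerance, nutrition habits, voiding and bowel movements and any signs of wound infection".

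Appendix B, the form itself, has columns for POD 1, POD 2 and condition at discharge. Its only tolerance row reads "Patient's tolerance to VAC", graded 1 to 4. It ends with "Time to first ambulation following surgery (specify unit please): Comments".

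Under Postoperative wound management, "the dressings in both groups will be removed on post-operative day(POD) # 5-7", or earlier for redness or signs of infection. The provider or research coordinator removes the dressing and repeats the swab. A blinded nurse practitioner or physician assistant then comes in to assess the wound.

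Allergy and intolerance have consequences elsewhere. Potential Problems and Alternative Strategies replaces the device with gauze and plans a sensitivity analysis for such crossover. Section 5 (Risks) opens its allergy item with "If at any time during the study the patient appears to have an allergic reaction to the incisional wound VAC device" and goes on to removal from the study. Section 4d lists intolerance and allergic reaction to the device among its stopping rules.

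**The concern.** The text gives the form one main job, and the form has no item for it. Nurses who complete Appendix B as printed will not be prompted to ask about itching, rash or blistering, so whether a mild reaction is recorded depends on what the patient volunteers and what the nurse writes under comments.

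The tolerance row also names a device that control patients do not have. In that arm it is likely to be left blank or filled in inconsistently. The trial would then have a tolerance grade for one arm and nothing to set beside it.

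What is at stake is the quality of the safety record, and the ability to say why patients came off the device and whether reactions were more common than with gauze and film.

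**Working it through.** No formula applies and the plan gives no figure to reproduce. The check compares the promised content with the form, row by row.

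**Rows on Appendix B.** Seal intact, drainage amount, drainage type, odor, erythema, ecchymosis, edema, seroma, incision intact, tolerance to VAC, NPO and voiding make 12 patient rows. Time to first ambulation and comments follow.

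**Promised topic against form:**

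| Topic in Follow Up, item 1 | Appendix B |
|---|---|
| Allergic reaction symptoms | No dedicated row (0 of 12); non-specific proxies are erythema, edema and the tolerance grade (3 rows), plus comments |
| Tolerance | One row, worded for the VAC |
| Nutrition | NPO |
| Voiding | Voiding |
| Bowel movements | No row (Appendix C asks about bowel habits, but at POD 30) |
| Signs of wound infection | Odor, drainage type, erythema, edema |

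Of six topics, two have no dedicated row (allergy, bowel movements) and one is worded for a single arm (tolerance).

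**Comparability of arms.** The control dressing is gauze with a transparent film (Swabbing section). Besides the tolerance row, the form's header asks for the width of foam used. The allergy provisions in Potential Problems, section 4d and section 5 all concern the device. A reaction to the control film or gauze therefore has no structured place, although Follow Up refers to the treatment option generally.

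**Visibility.** Five rows need a view of the site: erythema, ecchymosis, edema, seroma and incision intact. They are scheduled at POD 1-2, and planned removal is at POD 5-7. The interval is 5 − 2 = 3 days at the shortest and 7 − 1 = 6 days at the longest. The form does not say how to score these rows with the dressing on, so a *no* could mean absent or not seen.

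**Whether another contact supplies the missing question.** The POD 5-7 text covers infection and complications by CDC guidelines. Appendix C has redness, discoloration and an overall-experience grade at POD 30. Neither asks about symptoms while the dressing was worn. The list of signs for which patients should contact the hospital omits itching, rash and blistering. The sections on replacement, stopping and removal say what follows once a reaction is known, not how to ask about it.

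**The case against.** The strongest reply is that the form is not empty on this subject and does not stand alone. Erythema, edema, a graded tolerance row and comments, taken by a nurse in person, can register a local reaction. The discharge column allows a further entry, possibly after POD 2. Study Procedures, part b, says the dressing is monitored over five days, and allergy or intolerance is to be acted on whenever it appears. A device removal is identified by the removal itself, and the plan undertakes to report all protocol deviations. Known allergy to acrylic adhesives or silver is excluded at entry.

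Most of this stands, and it rules out several stronger readings that a reader might infer:

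- *The safety purpose is missed altogether, or the form cannot show a reaction.* The proxies and free text rule this out. Capture is non-specific, not absent.
- *Good tolerance could be reported because nobody was asked.* Device patients are asked for a tolerance grade.
- *Most of the wear period has no structured question.* Counting from the interview gives 3/5 = 60% to 6/7 = 86% of wear. That ignores the discharge column, and the upper end also assumes no POD 2 entry. The documents do not support a percentage.
- *The skin cannot be seen at POD 1-2.* This is partly inference. Skin at the dressing edge or under clear film may be visible, early removal is allowed, and section 5 envisages inspecting the skin edges.
- *Crossovers will be under-counted.* This is not shown, since they do not depend on Appendix B for detection.

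The reply does not supply the promised items or a tolerance grade that a control patient can answer. The five-day monitoring names no form.

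**Conclusion.** The point holds as a mismatch between the protocol text and its own form. Appendix B has no dedicated item for the symptoms that Follow Up ranks first, omits the promised bowel-movement item, and records tolerance in terms that fit one arm only. Allergic reaction is captured non-specifically, and tolerance cannot be compared between arms.

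The severity is minor. Allergy and tolerance are neither primary nor secondary outcomes, and the SSI analysis and sample size are untouched. The effect is on safety recording and on the documented reasons for crossover or removal from the study.

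This rests on two assumptions. The readable rows are taken to be the whole form: the table is broken in the text reviewed, but its rows appear twice and agree. Nurses are also assumed to follow the printed form; one who asks further questions unprompted would narrow the gap, but not in a way the data would show.

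**What to change.** Revise Appendix B to match Follow Up, item 1:

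- Add yes/no items for reaction symptoms at or around the dressing, such as itching, rash and blistering. The exact list is for the investigators to settle.
- Add the bowel-movement item.
- Reword the tolerance row as *tolerance of the dressing*, to be answered in both arms.
- Add a *not visible* code for items under an intact dressing.
- Repeat the reaction and tolerance items at the POD 5-7 removal, completed by the person who takes the dressing off. The blinded assessor should not complete or see them, because the answers could reveal the arm.

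These changes affect data fields only. They leave every rule on replacing the device or removing a patient as it is. The cost is a one-page form revision and about a minute more at each of two contacts that already exist.
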